## **ABSTRACT**

### **Background**

Plant-based analogues and substitutes for animal meat are receiving considerable attention within academia and the popular press. Once a niche product aimed at vegetarians, they are increasingly promoted to omnivores and meat-moderating “flexitarians”. Proponents view these new foods as a means of reducing livestock production and improving the environment, whilst industry sees opportunity to repurpose traditional and novel crops into high-value ingredients. To date, most research on meat alternatives has focused on public perception, processing technologies, hedonics and the consumer acceptability issues that underpin product development. There have been surprisingly few investigations into the nutritional, health and well-being consequences of consuming meat analogues over the short-term or long-term. The aim of our current trial is to investigate the digestion, absorption and utilisation of a meat-analogue meal in Millennial consumers and compare that to matched meals featuring pasture-raised, grain-finished beef or lamb.

### **Methods**

A cohort of healthy, young (20-34 years old) male participants will consume a single meal on four occasions in a treatment-crossover, blinded investigation. Each instance will be followed by four hours of repeated venous blood collection to assess the digestive and metabolic effects of the meal. The four meals include a popular commercial meat analogue comprising pea, bean and rice extracts plus plant fats and cellulose, or a mince from pasture-raised or grain-fed beef or grass-raised lamb. Blood plasma samples of the participants will be measured for changes in chylomicron fatty acid distribution, amino acid profile, neurotransmitter proteins, minerals, inflammatory markers and biomarkers of general health.

### **Discussion**

To our knowledge this is the first randomised controlled trial (RCT) comparing the acute nutritional effects of iso-caloric, blinded meals containing a plant-based meat analogue or pasture-fed-, grain-finished beef or lamb. The study provides proof of principle for only the effects of a single meal. Future work will translate these insights into longer-term, lifestyle interventions.

### **Trial Registration**

This study, registered as Universal trial number: U1111-1244-9426, will be carried out under the auspices of The University of Auckland. The trial has been granted ethical approval by the Ministry of Health, Health and Disability Ethics Committee (Ref: 19/STH/226).

Date and version: 24/07/20, 5

**Key Words:** protein, amino acid, diet, health, meat products, bioavailability

## ADMINISTRATIVE INFORMATION

Note: the numbers in curly brackets in this protocol refer to SPIRIT checklist item numbers. The order of the items has been modified to group similar items (see <http://www.equator-network.org/reporting-guidelines/spirit-2013-statement-defining-standard-protocol-items-for-clinical-trials/>).

**Table 1:** Trial Administrative Details

Title {1}	Acute Evidence of Digestive, Metabolic and Nutritional Differences in Beef, Lamb and Meat-Analogue Meals: A study protocol for a randomised control trial
Trial registration {2a and 2b}.	Universal trial number: U1111-1244-9426. ClinicalTrials.gov: 5000927, (pre-recruitment)
Protocol version {3}	24/07/2020, Version 5
Funding {4}	This research is funded by the Meat Industry Association Innovation Limited (a subsidiary of the New Zealand Meat Industry Association), Beef and Lamb New Zealand Limited and the New Zealand Ministry of Business, Innovation and Employment.
Author details {5a}	Refer to Table 3
Name and contact information for the trial sponsor {5b}	Auckland Uniservices, c/o The University of Auckland, [name]
Role of funder{5c}	The funder(s) have no involvement in the data collection, analysis and interpretation of the data; in the writing of the report; and in the decision to submit the paper for publication as contracted.

## INTRODUCTION

### Background and Rationale

A popular and common dietary trend is the reduction in red meat, and increase in meat alternatives. Whilst meat alternatives were once niche food products aimed at vegetarians, they are increasingly marketed to omnivores and “flexitarians”, thus contributing to a trend for reductions in red meat intakes [1]. While the environmental effects, consumer perceptions and acceptability of meat alternatives have been investigated [2, 3, 4], yet there is surprisingly a paucity of data comparing the nutritional and digestive differences to meat.

Red meat consumption contributes essential nutrients to the diet, including balanced amino acids, long chain fatty acids and complex lipids, vitamins (including B12) and minerals (including iron, zinc and selenium) [5]. Such nourishment comes in the context of a whole food that also includes health risk components, such as endogenous saturated fats, nitrates added to preserved meats, or heterocyclic amines formed during cooking [5]. Consequently, categorising a complex food as being either ‘good’ or ‘bad’ for health is now considered overly simplistic [6].

Dietary substitutes for red meat have a long history and new options are being actively developed. Most plant-based analogues attempt to replicate the taste and eating experience of meat, whilst delivering quality nutrition. The products' nutrition information panels (NIP) and label claims emphasise chemical analysis (primarily amino acid profiles) and draw comparisons to the acknowledged standard of muscle meat. This composition is indicative of potential nutrition, but it is not definitive, particularly for highly processed foods. The matrix of a food, its ingredients and structure, have marked effects on how well nutrients are actually absorbed and utilised. Few research studies have addressed the health outcomes of consuming novel meat analogues or compared them directly to traditional foods.

Red meat is also a complex food that reflects its origin and handling. Differences arise due to species, farming and feeding practices of the animals [7]. For instance, meat from ruminant animals raised on predominately pasture-based diets has higher levels of polyunsaturated fatty acids (PUFA) and related lipids derived from leaf oils (i.e. green grass) compared to meat from grain-fed animals, which accumulates the lipids of seed oils [8]. Research on the clinical implications of consuming these different fatty acid profiles is contradictory and may reflect health status and habitual patterns of meat consumption. Nevertheless in healthy consumers, pasture-raised meat increased both plasma and platelet concentrations of long-chain n-3 PUFA (LCPUFA) [9], supporting the effects of meat-derived fatty acids on health indices [10].

The LCPUFA subset found in red meat is drawing increasing attention as important bioactives for health, given their lipid-lowering properties, reductions in platelet aggregation, inflammation, and improvements in cognition and mood [11]. In the context of a Western diet where seafoods are minimal, the contribution of red meat to total LCPUFA intake can be substantial [12]. Research has shown that the LCPUFA of pasture-raised Wagyu was twice that of grain-finished Angus [8] and that it would contribute approximately 35-80% to the recommended adequate intake for men and women, respectively [13].

Meat is highly digestible and its nutrients are readily available. The qualities of grass- and grain-finished beef have not been directly compared to a plant-based meat analogue and lamb, outside of glycaemic and satiating responses [14]. Our proposed research will provide insight into the digestibility and nutrient delivery of these foods, and will quantify key metabolic responses to consuming a single meal. This study is a step towards understanding the nutritional, health and well-being consequences of meat analogues that may accrue from long-term repeated consumption.

## **Objectives**

To investigate the digestive responses to an acute intake of pasture-fed beef, grain-finished beef, lamb and a plant-based meat analogue consumed as a component of a mixed meal.

This study is part of a larger programme to understand the nutritional implications of consuming NZ, pasture-fed red meat as part of a balanced diet.

## **Trial Design**

A 4-arm randomised control trial using crossover design with equal allocation to each arm and adopting a non-inferiority framework.

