## **METHODS/DESIGN**

### **Study Setting**

The trial will be conducted at the University of Auckland Clinical Research Centre. The study is a randomised crossover trial to capture biological difference in postprandial nutrient dynamics. Research subjects will act as their own controls and will consume each meal on a separate occasion in random order. The study compares exemplars of pasture-fed New Zealand beef, grain-finished New Zealand beef, New Zealand lamb and a plant-based meat analogue. The pasture-fed beef was obtained from Angus Steers that had been fed exclusively on pastures (ryegrass and white clover mix) whereas the grain-finished beef was Angus steers that had been finished for an average of 122 days on a maize silage, barley wheat and straw ration. Marble score (3-4/9 on the Australian Grading System) [15] and pH (average 5.5) of the meat were consistent between production systems. The lamb will be sourced from New Zealand. The meat analogue has been selected from commercial varieties on the basis of its macronutrient profile (protein and fat) and appearance to best match that of meat.

The digestion and metabolism of key nutrients will be measured immediately after the ingestion of a single meal. This experimental setting will also be used to examine some subjective qualities of the meal experience, such as satisfaction score (i.e., liking, satisfaction, enjoyment, satiety, appetite) and gastrointestinal score (i.e., comfort, fullness, bloating, rumbling, flatulence, faecal urgency, diarrhoea).

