### **Sample size calculation**

The principal biomarker for calculation of sample size is postprandial change in LCPUFA concentrations in plasma chylomicrons (namely 20:4 n-6, 20:5 n-3, 22:5 n-3, 22:6 n-3). We estimate a sample size of 29 would enable the detection of a smallest worthwhile change of 0.5 mmol/L from baseline to 4 hours post meal consumption [19]. Pooled published data indicate an increase of ~3.9 mmol/L ( $\pm 2.8$  mmol/L) in chylomicron fatty acids post meal consumption. An effect size of 0.2 is used to calculate the smallest worthwhile effect. Recruitment will continue until 29 men have successfully completed the trial.

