## Outcomes (Primary and Secondary)

Following the consumption of a single meal:

Primary outcome variable

- Change in LCPUFA (18:2 n-6, 18:3 n-3, 20:4 n-6, 20:5 n-3, 22:5 n-3, 22:6 n-3) concentrations in the chylomicron fraction over 4 hours. Difference in the change between pasture-, grain-beef, lamb and plant-based alternative meat meals.

Secondary outcome variables

- Differences in other fatty acid (14:0, 16:0, 16:1 n-7, 18:0, 18:1 n-9, others) concentrations in the chylomicron fraction over 4 hours.
- Differences in the plasma amino acid (isoleucine, leucine, valine, histidine, lysine, methionine, phenylalanine, threonine, alanine, arginine, asparagine, aspartic acid, glutamic acid, glutamine, glycine, proline, serine, tyrosine, 3-methylhistidine, citrulline, hydroxyproline, ornithine, taurine, others) concentrations over the 4 hours.
- Differences in plasma neurotransmitter concentrations (phenylethyl amine, 3,4-dihydroxyphenylalanine, dopamine, 3-methoxytyramine, 3,4-dihydroxyphenylacetic

acid, homovanillic acid, norepinephrine, 3,4-dihydroxyphenylglycol, 3-methoxy-4-hydroxyphenylglycol, normetanephrine, epinephrine, metanephrine, vanillylmandelic acid, tryptophan, kynurenine, 5-hydroxytryptophan, serotonin, 5-hydroxyindoleacetic acid, alpha-aminobutyric acid, gamma-aminobutyric acid).

- Differences in minerals and haemoglobin concentrations.
- Change in inflammatory markers (TNF $\alpha$ , IL-1, IL-6, IL-8, IL-10, IL-13, hs CRP).
- Digestive differences based on genetic profile.
- Differences in subjective experience to the meal including fullness, satisfaction, gastrointestinal comfort scores among pasture-, grain- and plant-based alternative meat meals.
- Qualitative differences in the participant's opinions regarding future red meat consumption ("Participant insights").
- Adverse events, count score differences between meals.

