### **Trial Steering Committee and Availability of data and materials**

The principal investigator (PI) will be responsible for the project coordination and the research support will oversee the operational aspects of the trial. A scientific advisory group will regularly monitor the study implementation, as well as the data generation, documentation and reporting. Protocol amendments will be communicated by the PI to the ethics committee and clinical trial registration. Access to data will be granted to appropriate members of the research team and to authorised representatives from the host institution to monitor and/or audit the study and ensure compliance with regulations. Data will be made available to external academics on reasonable request.

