## Trial Status

Recruitment will commence October 2020.

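### The protocol declares a non-inferiority framework, but its sample size of 29 is justified by detecting a smallest worthwhile change, not by excluding a between-meal margin

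*Protocol*

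**What the plan says.** The Trial Design section is one sentence: "A 4-arm randomised control trial using crossover design with equal allocation to each arm and adopting a non-inferiority framework". This is the protocol's only reference to non-inferiority.

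The Sample size calculation section states that "a sample size of 29 would enable the detection of a smallest worthwhile change of 0.5 mmol/L from baseline to 4 hours" after the meal, and adds: "An effect size of 0.2 is used to calculate the smallest worthwhile effect". It cites pooled published data for an increase in chylomicron fatty acids of about 3.9 mmol/L, with ±2.8 mmol/L, and plans recruitment until 29 men have completed. It gives no alpha, sidedness, power or within-person correlation.

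The primary outcome, under Outcomes (Primary and Secondary), is the change in chylomicron LCPUFA over 4 hours, with the comparison given as "Difference in the change between pasture-, grain-beef, lamb and plant-based alternative meat meals".

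Two other sections describe the purpose. The Objectives section reads "To investigate the digestive responses to an acute intake of pasture-fed beef, grain-finished beef, lamb and a plant-based meat analogue", and the Study Setting section says "The study is a randomised crossover trial to capture biological difference in postprandial nutrient dynamics".

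**The concern.** A non-inferiority trial is sized to exclude a loss larger than a margin, in a stated direction, against a reference. The sample-size section is written for a different task, that of detecting an effect. It does not call 0.5 mmol/L a margin, and its wording ties that value to a change from baseline rather than to a contrast between two meals. The primary comparison is among four meals, with no direction.

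What is at stake is how a null result may be read. Under the declared framework, a finding of no clear difference between, say, the analogue and a meat meal could be reported as non-inferiority, although 29 was not justified for that claim. Under a difference framework, the same finding would be reported as an estimate with its confidence interval.

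**Working it through.** **Inputs.** From the Sample size calculation section: n = 29, target 0.5 mmol/L, effect size 0.2, and ±2.8 mmol/L. The protocol does not say that ±2.8 is a standard deviation, and it is quoted for chylomicron fatty acids rather than for LCPUFA. Assumptions made here: ±2.8 is an SD of the change; the correlation ρ between a man's responses to two meals is unknown; the SD of a between-meal difference is SD_d = 2.8 × √(2(1 − ρ)).

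**1. Where 0.5 may come from.** 0.2 × 2.8 = 0.56 mmol/L, and conversely 0.5 / 2.8 = 0.179. So 0.5 looks like a rounded standardised-effect threshold. Such a value could be adopted as a margin, but the section does not adopt it as one.

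**2. Can 29 be reproduced?** Not from the protocol's inputs alone. With n = (SD_d × (z_0.975 + z_0.80) / δ)²:
- SD_d = 2.8 (ρ = 0.5), δ = 0.5, two-sided 5%, 80% power: (2.8 × 2.802 / 0.5)² gives 247.
- Solving for n = 29: SD_d = 0.5 × √29 / 2.802 = 0.96, which corresponds to ρ of about 0.94.
- A four-meal repeated-measures ANOVA with f = 0.2, ρ = 0.6 and 80% power returns 29. Its form, ρ and power are all assumed, and it too tests for a difference.

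These results bracket what might have been done. They do not show 29 to be wrong.

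**3. Does the framework change n?** Take one contrast with a margin of 0.5, a true difference of 0 and one-sided 0.025. The formula in step 2 applies unchanged, with the margin in place of δ. By the noncentral t distribution at n = 29, non-inferiority power is 0.151 and two-sided 5% difference-test power is 0.153 at SD_d = 2.80. Both are 0.312 at SD_d = 1.77 (ρ = 0.8). The small gap in the first pair is the far tail of the two-sided test. For one contrast, the framework makes essentially no difference to n.

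**4. The two readings of 0.5.**
- As a change within a meal, it is not a between-meal quantity, so it fits neither a non-inferiority contrast nor the primary contrast.
- As the smallest between-meal difference in change, it fits the primary contrast, but the stated aim is still to detect it, not to exclude it.

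On either reading the stated basis is detection.

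**5. What the label does to a null result.** Suppose the observed difference is 0. The 95% half-width is t_0.975,28 × SD_d / √29.
- SD_d = 0.885 (ρ = 0.95): 2.048 × 0.885 / 5.385 = 0.34. The interval −0.34 to +0.34 lies inside a 0.5 margin and would be called non-inferior.
- SD_d = 2.80 (ρ = 0.5): 2.048 × 2.80 / 5.385 = 1.07. It would not be called non-inferior.

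Under a difference framework, both would be reported as estimates with their intervals. So the label decides whether a positive claim is available, and at the favourable end it does so without a margin having been set as the basis of n.

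**The case against.** The strongest reply is that this is a conflict of vocabulary. The sample-size section states no hypothesis or test, a smallest worthwhile effect is the kind of quantity that can serve as a margin, and the SAP, which was not available here, may name the margin, reference meal and direction. Much of this stands. The absence of those details from the protocol is not itself the point, and the inference from the wording is one of mismatch, not of logical impossibility. What the reply does not remove is that the protocol fixes both the framework and the basis of n, and the two do not agree. A margin added later would not change how 29 was justified.

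A reader might infer that the trial is underpowered. The documents do not support that: the result depends on an unstated correlation, an SD of unstated type, and an unstated alpha and power. Step 3 also shows that, for one contrast, the choice of framework barely moves n.

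A reader might also infer that the two frameworks read the same interval in opposite ways, or that a difference framework would let it say nothing. That is too strong. An interval of −0.34 to +0.34 is informative under either framework, since it shows which differences the data are compatible with.

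Finally, the Objectives and Study Setting wording might be taken as proof that non-inferiority was never meant. Investigating responses and capturing differences are both compatible with non-inferiority, so those sections are background only.

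**Conclusion.** The point holds as a mismatch between the declared framework in Trial Design and the basis of n = 29 in Sample size calculation, with the undirected primary contrast on the side of the latter. It rests on the wording of those sections and needs no assumption about SD or correlation. Its effect is on the claim that a null result could support, not on conduct or on a demonstrated error in n. It should be fixed, and it is not grounds to say that 29 is too few. Confidence is high for the mismatch. How much it matters in practice depends on the result and on what the SAP says about reporting it.

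**What to change.** Reconcile the two sections before recruitment. The Trial Status section says "Recruitment will commence October 2020". The sponsor knows which hypothesis was intended.

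**(a) If differences are the aim.** In Trial Design, replace the closing phrase on non-inferiority with: *estimating and testing differences between meals, reported with 95% confidence intervals; failure to find a difference will not be reported as non-inferiority or equivalence*. In Sample size calculation, state whether 0.5 mmol/L is a within-meal change or, to match the primary outcome, a between-meal difference in change. The cost is one sentence and one clarification, with no change to conduct. The downside is that the sponsor gives up a non-inferiority claim.

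**(b) If non-inferiority was intended.** Rest the calculation on a between-meal margin against a named reference meal, and restate the power that n = 29 gives for it from the sponsor's own SD and correlation. The cost is a justified margin and a new calculation; n may or may not rise.

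The amendment route already exists: "Protocol amendments will be communicated by the PI to the ethics committee and clinical trial registration". The illustrative figures in the working rest on assumed inputs and should not be put into the protocol.

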## **METHODS/DESIGN**

### **Study Setting**

The trial will be conducted at the University of Auckland Clinical Research Centre. The study is a randomised crossover trial to capture biological difference in postprandial nutrient dynamics. Research subjects will act as their own controls and will consume each meal on a separate occasion in random order. The study compares exemplars of pasture-fed New Zealand beef, grain-finished New Zealand beef, New Zealand lamb and a plant-based meat analogue. The pasture-fed beef was obtained from Angus Steers that had been fed exclusively on pastures (ryegrass and white clover mix) whereas the grain-finished beef was Angus steers that had been finished for an average of 122 days on a maize silage, barley wheat and straw ration. Marble score (3-4/9 on the Australian Grading System) [15] and pH (average 5.5) of the meat were consistent between production systems. The lamb will be sourced from New Zealand. The meat analogue has been selected from commercial varieties on the basis of its macronutrient profile (protein and fat) and appearance to best match that of meat.

The digestion and metabolism of key nutrients will be measured immediately after the ingestion of a single meal. This experimental setting will also be used to examine some subjective qualities of the meal experience, such as satisfaction score (i.e., liking, satisfaction, enjoyment, satiety, appetite) and gastrointestinal score (i.e., comfort, fullness, bloating, rumbling, flatulence, faecal urgency, diarrhoea).

### **Eligibility criteria**

All participants will be omnivores willing to consume both red meat and plant-base alternatives for the purposes of the trial. Those with chronic health conditions, hyperlipidaemia, obesity (BMI  $\geq$  30), use of medications (except occasional use of NSAIDs and antihistamines), history of anosmia and ageusia (issues with taste and smell), current dieting or disordered eating pattern and smoking tobacco or recreational drugs will be excluded from participating. Participants will complete an on-line screening that includes the Three-factor Eating Questionnaire-R18 (TFEQ) and a health survey. Participants with a TFEQ score greater than 75% will be excluded from participating on the basis their perception of food is potentially influenced by underlying psychological issues.

